# 11. ANTI-CANCER ACTIVITY ANALYSES

An abbreviated efficacy analyses will be performed because of the early stopping of study. All analyses will be based on the All Treated population as defined in Section 6 unless otherwise specified.

The primary efficacy endpoint of overall response rate (ORR) determined by investigator according to standard RECIST v1.1 (E.A. Eisenhauer, 2009). Summary of Investigator

assessed best response by dose group and for all subjects will be provided. The duration of response is defined as time from first documented evidence of CR or PR until first documented disease progression or death due to any cause, which will be calculated for subjects with confirmed CR or PR per RECIST v1.1 and listed in the listing of investigator assessed response. The measurement of target lesion and non-target lesion will be listed, separately.

Listings of tumour markers and other measures of clinical benefit will be provided.

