## $H_A:p \ge 30\%$

Starting with a group of 12 subjects and allowing for a maximum sample size of 30, this design will have a type I error rate ( $\alpha$ ) of 0.15 and 94% power. Group enrollment will be stopped early for futility if the predictive probability of success is less than 6%. The trial would not stop early for success. The Bayesian Prior was Beta (0.2, 0.8), a weak prior with a mean response rate of 20%. The group outcome will be considered successful if the posterior probability of (P >0.10 | observed data) is ≥80%. The futility boundary described in the Protocol Section 13.6.2 was calculated based on the optimizing criterion of maximizing the power under the alternative hypothesis.

Under the null hypothesis, the expected sample size is 20 subjects and the probability of early termination is 77%. Under the alternative hypothesis, the expected sample size is 29 subjects and the probability of early termination is 5%.

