# 19.1.2. Efficacy Figures and Tables

# Tables

No.	Population	IDSL / TST ID / Example Shell	Title	Programming Notes	Deliverable
10.1	All Treated	RE1a	Summary of Investigator Assessed Best Response (RECIST 1.1 Criteria)	Best Resp. only	SAC
10.2	All Treated	RE5	Listing of Investigator-Assessed Tumor Responses (RECIST1.1 Criteria)		SAC
10.3	All Treated	LA2	Listing of Target Lesion (RECIST v1.1)		SAC
10.4	All Treated	LA3	Listing of Non-target Lesion (RECIST v1.1)		SAC

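### SAP 5.2 keeps a success rule for each Part 2 histology group, but the planned efficacy display gives no group-level response rate, interval or success/futility outcome

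*SAP*

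**What the plan says.** **The rule.** SAP 5.2 and Protocol 13.2.2 test, in each Part 2 group, a response rate of at most 10% against at least 30%. The design is described as "Starting with a group of 12 subjects and allowing for a maximum sample size of 30", with a type I error "of 0.15 and 94% power". The prior: "The Bayesian Prior was Beta (0.2, 0.8), a weak prior with a mean response rate of 20"%. The success criterion: "The group outcome will be considered successful if the posterior probability of (P >0.10 | observed data) is ≥80"%. Enrolment is "stopped early for futility if the predictive probability of success is less than 6"%. There is no early stop for success. Protocol 13.6.2 (Table 15, Figure 1) turns the futility rule into responder counts at 12 to 30 subjects.

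**The reporting.** SAP 11 names ORR as the primary efficacy endpoint and announces an abbreviated analysis because of early stopping. Its only efficacy summary is investigator "assessed best response by dose group and for all subjects will be provided". In SAP 19.1.2 this is Table 10.1, with the programming note "Best Resp. only"; the other efficacy displays are listings. SAP 7.1 gives Part 2 a single column at 30 mg/kg, with no split by tumor type.

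**What the protocol promised.** Protocol 13.1.2 says observed response rates will be described in each group, and 13.7.1 says response data will be summarized by cohort or group. ORR is the Part 2 secondary endpoint for clinical benefit (Protocol 2.2).

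**The concern.** The unit of the decision rule is the histology group; the unit of the planned summary is the dose. For Part 2 the two do not meet: melanoma, gastric, head and neck, and lung subjects fall into one column. Following the SAP, the report would state the rule and then show nothing that says how each group fared under it.

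Early stopping makes this matter more. A group may have closed because it crossed the futility boundary, or because the study ended. The first is a result under the design; the second is not. Without a group-level count, an interval and a stated outcome, a low response count looks the same in both cases. A reader then cannot easily separate evidence that a group's rate is below 30% from too little data to say.

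**Working it through.** **Inputs.** Null rate 10%, target rate 30%, prior Beta(0.2, 0.8), success threshold 80%, futility threshold 6%, group size 12 to 30 (SAP 5.2); futility boundary of 0/12, 1/16, 2/22, 3/27, 4/30 (Protocol Table 15).

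**Step 1: the plan's own figures.** With x responders in n subjects the posterior is Beta(0.2 + x, 0.8 + n − x).
- At n = 30, P(p > 0.10) is 0.689 for 4 responders and 0.851 for 5. Success at full enrolment therefore means at least 5/30.
- Applying the 6% limit to the beta-binomial predictive probability of reaching 5/30 returns exactly the Table 15 boundary.
- An exact binomial recursion over that boundary gives:

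| Quantity | Stated | Recomputed |
|---|---|---|
| Type I error at 10% | 0.15 | 0.1486 |
| Power at 30% | 94% | 94.5% |
| Expected size, null | 20 | 20.05 |
| Early termination, null | 77% | 76.7% |
| Expected size, alternative | 29 | 29.4 |
| Early termination, alternative | 5% | 4.6% |

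The design is sound as stated. The gap is in reporting.

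**Step 2: match the rule to the displays.**

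| Needed to report the rule | Planned? |
|---|---|
| Responders and N by histology group | No: one Part 2 column (SAP 7.1) |
| Response percentage | Probably, pooled: SAP 8.1 uses n and percent, SAP 9.1 fixes the denominator |
| Interval for the rate | None named |
| Posterior, or success/futility outcome | None named |
| Handling of a group closed below 30, boundary not crossed | None stated |

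**Step 3: what an interval would add.** The documents give no group sizes or responder counts, and no confidence level for ORR, so these are illustrations at an assumed two-sided 95% level. With no responders the exact upper limit is 1 − 0.025^(1/n):
- n = 6: 45.9%
- n = 10: 30.8%
- n = 11: 28.5%
- n = 12: 26.5%

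A response table shows 0% in all four cases, but only the last two exclude 30%. The cut-off depends on the level. With no responders, the smallest n whose upper limit falls below 30% is 11 at two-sided 95%; 9 at one-sided 95% (28.3%); 8 at the design's 6% type II error (29.6% or 29.7% by rounding: 1 − 0.06^(1/8) = 0.2965); and 6 at one-sided 85% (27.1%).

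**Step 4: why the posterior alone is unsafe below 30.** Under the same prior, 1/3 gives 0.815 and 2/8 gives 0.859, both above 80%. If the true rate is 10%, results at least this good occur with probability 1 − 0.9³ = 0.27 and 1 − 0.9⁸ − 8(0.1)(0.9⁷) = 0.19. Both exceed the design's 0.15.

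**The case against.** The abbreviation is deliberate and disclosed. Part 2 is primarily about safety, and ORR is a secondary endpoint for preliminary evidence. Table 10.2 lists every subject's response, so a reader who knows each subject's tumor type could count responders and calculate an interval. That stands as mitigation, and it keeps the point below a mandatory correction. It does not replace a planned group summary that the protocol promised.

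Two stronger readings are tempting and should be resisted.
- **That only counts, and no response rate, will be shown.** A reader might infer this from "Best Resp. only". The documents do not support it: SAP 8.1 reports categorical data as n and percent, and SAP 9.1 keeps unevaluable or missing responses in the denominator as non-responders. Table 10.1 follows a sponsor library shell (RE1a) that is not reproduced, so what the note removes is unknown.
- **That the rule is never evaluated.** Protocol 13.6.2 compares responder counts with Table 15 during enrolment, Figure 1 covers every size from 12 to 30, and at 30 the count rule is the success rule. Below 30 the design makes no success decision, so none is omitted there. What is missing is the reporting of these outcomes in the SAP. SAP 4.1 plans no formal interim analysis, and its description covers only the Part 1 escalation reviews.

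**Conclusion.** The point holds as a reporting gap. The plan keeps a per-group decision rule and a per-group promise, but specifies no per-group response rate, no interval and no outcome, and it is silent on groups cut short by study closure. Followed as written, it would not answer its own question about activity in each histology group.

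How much this matters depends on group sizes at closure, which the documents do not give. If groups closed with about ten subjects or fewer and no responders, a two-sided 95% limit would not exclude 30%; at less strict levels that threshold moves down, with exclusion starting at n = 6 to 9. If every group crossed the futility boundary or reached 30, the loss is mainly of transparency. The design calculations are not in question. This should be corrected, but it does not touch the primary safety analysis.

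**What to change.** Add to Table 10.1, or as a companion table, one row per Part 2 histology group with:
- N and confirmed responders;
- ORR on the SAP 9.1 denominator;
- an exact (Clopper-Pearson) 95% confidence interval;
- the outcome, as one of three: futility boundary crossed; success (at least 5/30, equivalent to a posterior probability of at least 80% under Beta(0.2, 0.8)); or not assessable, because the group closed before 30 without crossing the boundary.

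If the posterior is also shown for a group below 30, label it descriptive and do not set it against 80%.

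The cost is one small table and a sentence in SAP 11. It needs a breakdown by histology group that SAP 7.1 does not now define, but it uses data already collected.

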# 12. SAFETY ANALYSES

Unless otherwise specified, all the safety analyses will be based on the All Treated population as defined in Section 6 and summaries will include all events or assessments collected during the study.

The lists of displays for safety analyses, including population to use for each display, are shown in Section 19 of the RAP.

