8.5. Time Period and Frequency of Detecting AEs and SAEs

The investigator or site staff is responsible for detecting, documenting and reporting events that meet the definition of an AE or SAE.

AEs will be collected from the time the first dose of study treatment is administered until 28 days following discontinuation of study treatment.

SAEs will be collected over the same time period as stated above for AEs. In addition, any SAE assessed **as related** to study participation (e.g., protocol-mandated procedures, invasive tests, or change in existing therapy), study treatment or GSK concomitant medication must be recorded from the time a subject consents to participate in the study up to and including any follow-up contact. All SAEs will be reported to GSK within 24 hours, as indicated in Section [8.5.2](#).

After discontinuation of study treatment, the investigator will monitor all AEs/SAEs that are ongoing until resolution or stabilization of the event or until the subject is lost to follow-up. At any time after 28 days the investigator may report any AE that they believe possibly related to study treatment.

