# 12.2. Adverse Events

Adverse events (AEs) will be graded according to the CTCAE, Version 4.0. Adverse events will be coded to the preferred term (PT) level using the Medical Dictionary for Regulatory Affairs (MedDRA dictionary).

The relationship between MedDRA SOC, PT, and Verbatim Text will be displayed.

An overview summary of AEs, including counts and percentages of subjects with any AE, AEs related to study treatment, AEs leading to permanent discontinuation of study treatment, AE leading to dose reductions, AEs leading to dose interruptions, SAEs, SAEs related to study treatment, fatal SAEs, and fatal SAEs related to study treatment will be produced.

The following two types of summaries for AEs and drug related AEs will be provided:

- Summary of all AEs by frequency, which is a summary of the number and percentage of subjects with all treatment emergent AEs. Adverse events will be grouped by preferred term and sorted in descending order based on total incidence in all treatment groups.
- Summary of all AEs by maximum toxicity grade, which is a summary of the number and percentage of subjects with all treatment emergent adverse events by intensity or grade. Relevant treatment emergent adverse events will be grouped by the preferred term, and sorted in descending order based on total incidence in all treatment groups.

Treatment emergent AE is defined as adverse events which occur or worsen on or after date and time of first dose of investigational product.

A study treatment-related AE is defined as an AE for which the investigator classifies the relationship to study treatment as "Yes". A worst case scenario approach will be taken to handle missing relatedness data, i.e. the summary table will include events with the relationship to study treatment as 'Yes' or missing. The summary table will be displayed in descending order of total incidence by PT only.

All AEs will be listed. Additionally, a listing of subject IDs for each individual AE will be produced.

A listing of adverse events recorded as dose-limiting toxicities will be provided.

Listing of adverse events for subjects with grade 3 or higher AEs will be provided. In addition, a summary table of non-serious adverse events by system organ class and preferred term with occurrences  $\geq 5\%$  will be generated.

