## 12.4. Deaths and Serious Adverse Events

A listing by subject of all deaths will be produced. Primary cause of death, subreason of death, date of death and time from last dose will be listed for each subject who died.

All SAEs will be tabulated based on the number and percentage of subjects by frequency and maximum grade. SAEs are included in the listing of all adverse events. A supportive listing with all SAEs will be generated including fatal SAEs.

In addition, summary table of serious adverse events for all subjects by system organ class and preferred term including drug-related status and fatal status will be generated.

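### The SAE tables and the AE overview carry no treatment-emergent limit, so serious screening-procedure events before any drug can count in a dose column; the treatment-emergent definition also has no end

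*SAP*

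**What the plan says.** **Collection (Protocol section 8.5).** The base rule is that "AEs will be collected from the time the first dose of study treatment is administered until 28 days following discontinuation of study treatment". The same window is then set for serious events: "SAEs will be collected over the same time period as stated above for AEs". Two provisions extend beyond that window. One covers SAEs judged to have a link "to study participation (e.g., protocol-mandated procedures, invasive tests, or change in existing therapy), study treatment or GSK concomitant medication". Whatever its timing, such an event "must be recorded from the time a subject consents to participate in the study up to and including any follow-up contact". For non-serious events the extension is voluntary: "At any time after 28 days the investigator may report any AE that they believe possibly related to study treatment".

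**Reporting (SAP sections 12, 12.2 and 12.4).** Section 12 makes inclusion of everything collected the default ("summaries will include all events or assessments collected during the study") unless a later section says otherwise. Section 12.2 does so for four displays: AEs and drug-related AEs, each by frequency and by maximum grade, are limited to treatment-emergent events. The definition is: "Treatment emergent AE is defined as adverse events which occur or worsen on or after date and time of first dose of investigational product". It has a start but no end. For serious events section 12.4 says only: "All SAEs will be tabulated based on the number and percentage of subjects by frequency and maximum grade". Neither that section, nor the description of the AE overview in 12.2, nor the display list (Tables 11.10, 11.11, 11.12 and 11.22) adds a time limit.

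**Time periods (SAP section 9.3.1).** AEs, SAEs and deaths are assigned to pre-therapy, on-therapy (first dose to last dose plus 28 days) and post-therapy. No AE or SAE table is said to use the assignment.

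**The concern.** AEs and SAEs are among the primary endpoints in both parts. Complete collection runs only from first dose to 28 days after discontinuation; outside it, an event reaches the database because someone judged it related to something. Tables that mix these periods without saying so can mislead in two ways.

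First, a serious complication of a protocol procedure, recorded before any drug is given, would appear under a dose label. A fresh pre-treatment tumor biopsy is required in the PK/PD cohorts and in Part 2 and strongly encouraged in the escalation cohorts (footnote 5 of Protocol Tables 7 to 12), so the situation is foreseeable. Protocol section 13.4.6 treats pre-dose safety assessments as screening, and the tables would blur that line.

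Second, an unrelated event starting after the 28-day window is not collected under the base rule, while a possibly related one can be. An open-ended treatment-emergent definition lets these selected reports into the same counts as the completely collected ones.

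**Working it through.** The plan states no AE or SAE rate and no related share, so there is no figure to reproduce. The check sets collection against table scope and then works out direction and scale.

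**Step 1: what is collected and where it is counted**

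| Period | Collected | AE and drug-related AE tables | SAE tables and overview |
|---|---|---|---|
| Consent to first dose | SAEs related to participation, study treatment or GSK concomitant medication; no non-serious AEs | Excluded (treatment-emergent rule) | Counted, if the subject is later dosed |
| First dose to 28 days after discontinuation | All AEs and SAEs | Counted | Counted |
| Later | Related SAEs; other AEs if the investigator believes them possibly related and reports them | Counted (no end to the definition) | Counted |

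Subjects never dosed are outside the All Treated Population (SAP section 6).

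**Step 2: effect of one pre-dose SAE on incidence**

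Protocol Table 3 plans at least 3 escalation subjects per dose level from Cohort 2 on, and up to 3 PK/PD subjects. SAP section 7.1 pools groups with the same dose and frequency. A Part 1 column therefore has about n = 3 to 6 on planned sizes; the 1.4 mg/kg column, planned with a minimum of 1, is left out. If the subject has no other SAE, the shift is 1/n:

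- n = 3: 1/3 = 33 percentage points
- n = 6: 1/6 = 17 percentage points
- for contrast, a Part 2 group at its planned maximum of 30: 1/30 = 3.3 percentage points

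**Step 3: effect on the related share**

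SAP section 12.2 counts an event as related if its relationship to study treatment is Yes or missing. Let s be subjects with an SAE in the complete window, r those among them with a drug-related SAE, a subjects whose only SAE is a pre-dose procedure event, and b subjects whose only SAE is a late drug-related one.

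Related share = (r + b)/(s + a + b). It exceeds r/s only if b/a > r/(s − r).

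Assumed counts, for direction only: N = 30 treated, s = 10, r = 3.

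- Baseline: 3/10 = 30.0%
- a = 1, b = 0: 3/11 = 27.3% (SAE incidence rises from 10/30 = 33.3% to 11/30 = 36.7%)
- a = 0, b = 1: 4/11 = 36.4% (related SAE incidence rises from 3/30 = 10.0% to 4/30 = 13.3%)
- a = b = 1: 4/12 = 33.3%
- threshold: b/a > 3/7 = 0.43
- a = 1, b = 0, with relatedness missing and so imputed as Yes: 4/11 = 36.4%

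A pre-dose procedure SAE lowers the related share unless its relatedness field is empty. Only late related events raise it.

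**The case against.** Several objections have force.

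- **The default yields to specific text.** For the AE and drug-related AE frequency and grade tables it does, and pre-dose non-serious AEs are not collected at all. A reader might infer from section 12 that every AE summary includes pre-dose events; section 12.2 rules that out. The gap is confined to the SAE tables and the overview.
- **The SAE tables share display shells (AE3, OAE07) with the treatment-emergent AE tables, and listings of all SAEs exist.** A programmer might apply the same limit, but none is written for these tables, and a listing does not correct a table's incidence.
- **Related has two meanings.** A reader might infer that screening SAEs inflate the drug-related share because they were collected as related. Protocol section 8.5 includes relation to participation; the tables count relation to study treatment. Step 3 shows the share falling.
- **The number of pre-dose SAEs is unknown.** A reader might multiply the 141 planned biopsy subjects (120 in Part 2 plus 21 PK/PD) by a complication rate. The documents give no such rate, 141 is a planned maximum, and SAP section 11 says the study stopped early. A serious complication may prevent dosing, and a biopsy at pre-screening is taken under a separate consent and may precede SAE collection. No expected count is supportable. Nor is a share of events: the planned tables report subjects.
- **Late events should not be cut.** This stands. Protocol section 3.6.3 predicts a half-life of about 10 to 14 days after repeated dosing, so 28 days is 28/14 = 2 to 28/10 = 2.8 half-lives. Dropping later related SAEs from the tables of a first-in-human antibody trial would hide drug effects.

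**Conclusion.** The point holds for the SAE tables and the AE overview: as written, a serious screening-procedure event in a later-dosed subject counts under a dose. One such subject with no other SAE moves a Part 1 column of 3 to 6 subjects by 17 to 33 percentage points. That range rests on planned cohort sizes and on one event occurring; it says nothing about how often it would occur. The consequence is higher SAE incidence. It is not a higher drug-related share, except where missing relatedness is imputed as Yes.

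The open end of the treatment-emergent definition is a second, separate weakness, and it reaches the AE tables as well. Late collection favors related events, so the bias in the related proportion is upward, but its size cannot be computed from the documents; the 30.0% to 36.4% example uses assumed counts. The remedy is to show the late events for what they are. The documents do not support treating the 28-day boundary as a reason to exclude them.

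The correction is worth making because it concerns primary-endpoint tables and costs little. It does not affect the design.

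**What to change.** In SAP sections 12.2 and 12.4, and in the programming notes for Tables 11.10, 11.11, 11.12 and 11.22:

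1. Apply the section 12.2 rule (onset or worsening at or after the date and time of first dose) to every SAE table and to the AE overview.
2. Put pre-dose SAEs in a separate listing.
3. Use the section 12.2 date-and-time rule for the lower bound, not the section 9.3.1 on-therapy flag. That flag counts the whole of Day 1 as on-therapy for AEs, while Part 1 skin biopsies are taken pre-dose on Day 1 (Protocol Tables 7 to 11).
4. Keep events with onset more than 28 days after the last dose in the tables, but identify them in their own row or a footnote saying that collection in that period was limited to events thought related. Take the boundary from the end of the on-therapy period. The post-therapy category in 9.3.1 starts only at 45 days or 5 half-lives, so it would miss events between day 28 and that point.

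The cost is one filter, one listing, a row or footnote, and a few sentences of SAP text. Data collection does not change, and no event is lost from the report.
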